4.2. Treatment Arms and Duration

The total duration of subject involvement is up to 16 weeks (Screening to Follow-up) as described below:

- Screening: Screening will occur at least one week prior to but not more than 30 days prior to washout.
- ESA Washout: Subjects that meet eligibility criteria will begin the 2-week ESA washout at Week -2.
 - This should be timed such that this day occurs on the date that would have been the next scheduled dose of ESA (or as close as practicable).
 - For subjects with a three-times weekly dialysis schedule, this day must not occur on the first dialysis session of the week (e.g., if Monday-Wednesday-Friday schedule, the study visit cannot be on Monday).
 - For subjects with a four- to five-times weekly dialysis schedule, this day can be on any hemodialysis session of the week.
- Randomization & Acute Challenge 1 (Day 1): Subjects will be randomized 1:1 to two treatment arms as described in [Table 1](#) and will begin a 24-hr Acute Challenge where the acute BP effects of daprodustat and epoetin alfa will be

evaluated. This challenge will be initiated promptly following the subject's dialysis session.

- **Hgb Maintenance Period:** Subjects randomized to daprodustat will start an 8-week Hgb maintenance period based on a starting dose and dose adjustment algorithm as described in Section 6.4.1. Subjects randomized to epoetin alfa will begin an 8-week Hgb maintenance period where Hgb will be managed in accordance with local labelling.
- **Acute Challenge 2:** At the end of the 8-week Hgb maintenance period, subjects will repeat the procedures of Acute Challenge 1 utilizing the same treatment administered in Acute Challenge 1. This challenge will be initiated promptly following the subject's dialysis session.
- **Follow-up:** A Follow-up visit will be scheduled to occur 14 ± 3 days after completing treatment.

Table 1 Treatment Arm Descriptions

Treatment Arm	Acute Challenge 1	Hgb Maintenance Phase	Acute Challenge 2
A	100 U/kg IV epoetin alfa	IV epoetin alfa according to label	100 U/kg IV epoetin alfa
B	24 mg daprodustat	QD daprodustat according to dose adjustment algorithm (Section 6.4.1)	24 mg daprodustat

4.3. Type and Number of Subjects

The study will enroll hemodialysis-dependent subjects with anemia associated with CKD currently treated with an ESA. Subjects with Hgb values of 8.5 to 11.5 g/dL, inclusive at both Screening and Day 1, are eligible, and the subjects must currently be on an ESA product.

[figure not shown]
Approximately 124 subjects will be screened to achieve approximately 62 randomized and 50 evaluable subjects for a total of 25 evaluable subjects per treatment group.

If subjects prematurely discontinue the study, additional replacement subjects may be randomized and assigned to the same treatment arm at the discretion of the Sponsor in consultation with the investigator.

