6.2. Treatment Assignment

Subjects will be stratified by prior ESA dose (as outlined in Section [4.1](#)) and randomized 1:1 to receive open-label oral daprodustat or IV epoetin alfa. A central randomization approach will be used due to the small sample size and to protect against potential selection bias due to the open-label design. Once a randomization number has been assigned by an Interactive Voice/Web Response System (IVWRS) at time of Randomization, it must not be re-assigned.

Subjects will be assigned to study medication in accordance with the randomization schedule generated by Clinical Statistics, prior to the start of the study, using validated internal software.

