9.2. Sample Size Considerations

9.2.1. Sample Size Assumptions

It is expected that 31 subjects will be randomized into each treatment arm. Assuming a 20% withdrawal rate during the Hgb Maintenance Period, there will be 25 subjects per treatment arm that will undertake Acute Challenge 2. The study will continue to recruit subjects until it is projected that 25 subjects per treatment arm complete and pass QC for Acute Challenge 2.

Assuming a 5% significance level and a true standard deviation (SD) of 16 mmHg for average SBP over 6 hours, a sample size of 25 subjects per treatment group will provide greater than 90% power to detect a -15 mmHg difference between treatment groups. Under these assumptions, statistical significance will be obtained if there is more than a 9.1 mmHg mean difference observed in favor of daprodustat.

Table 6 Power and Half-width of 95% CI for pair-wise comparisons, assuming a 16 mmHg SD for average SBP over 6 hours

Challenge	Expected Number of Subjects per Treatment Group	Power to detect 15 mm Hg difference	Half-Width of 95% CI ²
Acute Challenge 1	31	95%	8.1 mmHg
Acute Challenge 2 ¹	25	90%	9.1 mmHg

¹ Primary Comparison² Minimal detectable effect

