9.2.3. Sample Size Re-estimation or Adjustment

Subjects that withdraw prior to the Acute Challenge 2 assessment will be replaced so that 25 subjects per treatment arm complete Acute Challenge 2.

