### 4. ANALYSIS POPULATIONS

Population	Definition / Criteria	Analyses Evaluated
Screened	
 
All participants who were screened for eligibility
 
	
 
Screen Failures
 

Enrolled	
 
All participants who enter washout.
 
Participants will be analyzed according to the treatment to which they were randomized, if randomized.
 
	
 
Study Population, Safety
 

Safety	
 
All randomized participants who received at least one dose of study treatment.
 
This population will be based on the treatment the participant actually received.
 
Note: Participants who were not randomized but received at least one dose of study treatment should be listed.
 
	
 
Safety
 

Intent-To-Treat (ITT)	
 
All randomized participants [who received at least one dose of study treatment].
 
This population will be based on the treatment the participant was randomized to.
 
Any participants who receives a treatment randomization number will be considered to have been randomized.
 
	
 
Primary, secondary, and exploratory endpoints excluding PK endpoints
 

Per-Protocol (PP)	
 
All participants in the ITT population who comply with the protocol.
 
Protocol deviations that would exclude participants from the PP population are defined in Section 4.1 (Protocol Deviations) and Appendix 1: Protocol Deviation Management and Definitions for Per Protocol Population.
 
	
 
Sensitivity analysis of primary endpoint
 

CONFIDENTIAL

205665

Population	Definition / Criteria	Analyses Evaluated
	
 
The PP set will not be analysed if this population comprises more than 90% of the ITT population.
 
	
Pharmacokinetic (PK)	
 
All participants in the Safety population who had at least 1 non-missing PK assessment (Non-quantifiable [NQ] values will be considered as non-missing values).
 
	
 
All PK endpoints
 

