## 14.7. Appendix 7: Reporting Standards for Missing Data

### 14.7.1. Premature Withdrawals

Element	Reporting Detail
General	
 
Participant study completion (i.e. as specified in the protocol) was defined as a participant who has completed all phases of the study including the follow-up visit.
 
Participants that withdraw prior to the Acute Challenge 2 assessment or subjects who do not pass QC for Acute Challenge 2 will be replaced so that 25 participants per treatment arm complete and pass QC for Acute Challenge 2.
 
All available data from participants who were withdrawn from the study will be listed and all available planned data will be included in summary tables and figures, unless otherwise specified.
 
Withdrawal visits will be slotted as per Appendix 3: Assessment Windows or will be summarised as withdrawal visits.
 

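### The optional replacement clause lets a dropout's arm, and not the central 1:1 schedule, decide a replacement's arm in an open-label trial; the risk is probably small and the fix is cheap

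*Protocol*

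**What the plan says.** Protocol Section 4.3 and the synopsis (Type and Number of Subjects) provide that, after a premature discontinuation, "additional replacement subjects may be randomized and assigned to the same treatment arm at the discretion of the Sponsor in consultation with the investigator".

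Protocol Section 6.2 describes allocation: stratified by prior ESA dose, 1:1, open-label, through a central IVWRS. The central approach was chosen partly "to protect against potential selection bias due to the open-label design". "Subjects will be assigned to study medication in accordance with the randomization schedule generated by Clinical Statistics", and the schedule is made before the study starts. A number given "at time of Randomization, it must not be re-assigned".

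Three other places deal with making up the numbers, and none gives an allocation method:

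- Protocol Section 9.2.1: the study will "continue to recruit subjects until it is projected that 25 subjects per treatment arm complete and pass QC for Acute Challenge 2".
- Protocol Section 9.2.3: subjects who withdraw before Acute Challenge 2 "will be replaced so that 25 subjects per treatment arm complete Acute Challenge 2".
- SAP Section 14.7.1: "Participants that withdraw prior to the Acute Challenge 2 assessment or subjects who do not pass QC for Acute Challenge 2 will be replaced".

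The ITT definition in SAP Section 4 adds: "Any participants who receives a treatment randomization number will be considered to have been randomized".

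**The concern.** If the dropout fixes the arm, chance does not. The clause uses both verbs, randomized and assigned, but a subject whose arm is settled in advance has not been allocated by a 1:1 schedule. In an open-label trial the dropout's arm is known to the site, and the clause brings the investigator into the decision to replace. An investigator could therefore know the arm of an open slot before choosing whom to screen for it. That is the selection bias that Section 6.2 sets out to prevent.

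Entry leaves some room for judgement on the very quantity being measured: exclusion criterion 9 includes hypertension that the investigator regards as uncontrolled. The clause also does not require a replacement to come from the dropout's ESA stratum.

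Replacements would not be visible in the analysis. They have randomization numbers, so they count as randomized, and none of the sensitivity analyses in SAP Section 11.1.5.2 (per-protocol, imputed data, longer averaging windows) separates them.

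There is also a plain inconsistency. The synopsis and Section 4.3 make replacement optional and limit it to discontinuations. Section 9.2.3 makes it mandatory, and SAP Section 14.7.1 makes it mandatory and adds QC failures.

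**Working it through.** **Inputs.** From Protocol Section 9.2.1: 31 randomized and 25 evaluable per arm, 20% withdrawal, SD 16 mmHg, difference 15 mmHg, 5% level. Two-sided testing is from Section 9.4.1.

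**1. The plan's own figures.** Noncentrality = 15 / (16 × √(2/25)) = 15 / 4.525 = 3.31. With 48 degrees of freedom the critical t is 2.011, and power is 90.1% (stated: 90%). Half-width = 2.011 × 4.525 = 9.10 mmHg (stated: 9.1). Both reproduce.

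**2. How often replacement would be needed.** Take completers per arm, X, as Binomial(31, 0.80).

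- P(X ≥ 25) = 0.571 per arm, so for both arms 0.571² = 0.326. Replacement is needed in about two trials in three.
- Expected shortfall per arm, E[max(25 − X, 0)] = 0.976. Replacements can drop out too, so the expected total is 2 × 0.976 / 0.80 = 2.44.
- If every dropout is replaced once, which Section 4.3 would allow, the expected number is 62 × 0.20 = 12.4.
- If QC failures are also replaced, a failure rate is needed that the documents do not give. At an assumed 5%, the success probability is 0.76, the expected total is 4.8 and the chance of needing none is 13%. At an assumed 10%, these are 0.72, 7.9 and 4%.

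**3. Is same-arm replacement needed for power?** By the same noncentral t calculation with n₁ and n₂ completers:

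| Completers | Power |
|---|---|
| 25/25 | 90.1% |
| 27/25 | 91.2% |
| 24/26 | 90.1% |
| 22/28 | 89.7% |
| 23/25 | 88.8% |

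Modest imbalance costs very little, so the power target does not depend on directing subjects to an arm.

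**4. Cost of using the schedule.** This was simulated with assumptions that are not in the documents: 31/31 initial subjects, accrual of 0.5, 1 or 2 per week, additional subjects in 1:1 blocks of 4, no strata, dropouts spread evenly over the 8 weeks, and no screening or washout delay. Recruitment reopens whenever fewer than 25 are projected in either arm.

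| Accrual per week | Extra subjects, same-arm: mean (95th percentile) | Extra subjects, 1:1 schedule: mean (95th percentile) |
|---|---|---|
| 0.5 | 2.42 (7) | 3.97 (12) |
| 1 | 2.65 (8) | 4.13 (12) |
| 2 | 3.00 (9) | 4.50 (13) |

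The difference in means is about 1.5 subjects. The mean absolute difference in completers between arms is about 2.3 with the schedule and 1.1 with same-arm replacement. If recruitment stops for good once the projection is first met, at least one arm finishes below 25 in about 17–29% of runs. Waiting until 25 per arm have actually finished would take 7.5 to 19.5 extra subjects on average.

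**The case against.** The strongest reply is that steering would be hard in practice. The trial is multi-centre (Protocol Section 4.4) with central allocation. An investigator would have to know that the sponsor had opened a slot and expect their own patient to fill it before one from another site. Screening takes at least 7 days and washout 14, so anyone already in that three-week pipeline was chosen before the arm was known. ABPM is objective, eligibility deviations are barred (Section 5), and the ANCOVA adjusts for pre-Acute Challenge 1 SBP and prior ESA dose. Under SAP Section 14.6.6 only subjects with QC-passed recordings enter the pharmacodynamic outputs, so a replacement counts in the primary comparison only after a valid Acute Challenge 2.

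Most of this stands, and it is why the point is an improvement and not a serious defect. It does not remove the issue. An objective endpoint limits measurement bias, not selection at entry. The baseline SBP is one reading, so adjustment for selection on blood pressure is partial. Patients screened after the dropout do not have the pipeline's protection.

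A reader might infer that the ban on re-assigning numbers contradicts the replacement clause. It does not: a replacement given a new number satisfies both. Nor does the missing detail prove that replacements bypass the IVWRS, since a reserved concealed list could exist. The plan describes none, however, and the clause followed as written gives a non-random arm.

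**Conclusion.** The point holds as a conflict in the allocation rules. The replacement clause lets a dropout set a later subject's arm, while Section 6.2 relies on a central pre-generated schedule to prevent selection bias, and nothing described reconciles them. The exposure is about 2.4 subjects if only the shortfall is filled and about 12 if every dropout is replaced, assuming independent 20% withdrawal from 31 per arm. The clause is optional, so the number could also be zero.

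A reader might go further and conclude that the primary comparison is biased, or that the sample size is wrong. The documents support neither. The size and direction of any bias cannot be determined from them, and the stated power and half-width reproduce. It would equally be too much to say that schedule-based recruitment guarantees 25 per arm; that holds only if recruitment can reopen.

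**What to change.** 1. In the synopsis and Protocol Section 4.3, delete the words that send a replacement to the dropout's arm. State instead that any additional subject is allocated through the existing central IVWRS 1:1 schedule stratified by prior ESA dose.
2. Use one recruitment rule in the synopsis, Protocol Sections 4.3, 9.2.1 and 9.2.3, and SAP Section 14.7.1: recruit until 25 subjects per arm are projected to finish Acute Challenge 2 with a QC-passed recording, and reopen recruitment if the projection later falls below 25 in either arm. This also settles the optional-versus-mandatory wording and the treatment of QC failures.
3. If same-arm replacements have already been enrolled, flag them in the analysis dataset and add to SAP Section 11.1.5.2 a repeat of the primary model without them.

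The cost is a short amendment with the usual ethics review, about 1.5 more randomized subjects on average than same-arm replacement, and slightly less equal arms, both under the assumed accrual and block size. Power stays at about 90% provided recruitment can reopen; if it cannot, a 23/25 finish would give 88.8%. The sensitivity analysis needs no new data.

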4.4. Design Justification

This study will be an open-label, multi-center, randomized, parallel-group design in HD subjects with anemia associated with CKD. There will be a screening period, a 2-week ESA washout period, an initial 24-hour Acute Challenge, an 8-week Hgb-maintenance period, a second 24-hr Acute Challenge, and a follow-up visit 14 ± 3 days after completing treatment.

- This will be an open-label study since the primary endpoint (SBP by ABPM) is an objective measure and unlikely to be influenced by knowledge of the treatment received. Additionally, blinding of an injectable comparator and oral study drug is impractical in this case.
- A screening period will be used to assess Hgb stability in order to minimize the potential for enrolling patients with highly variable Hgb despite ESA treatment.
- In our previous daprodustat study experience in Phase 2b, HD-dependent subjects with anemia associated with CKD were administered placebo for 4 weeks, with a mean decrease between 0.61 and 0.72 g/dL in Hgb. No subject met either the Hgb stopping criterion or requiring rescue medication. Therefore, the risk of a subject meeting Hgb withdrawal criteria is considered low during this phase.
- The Acute Challenge days have been designed to be consistent with the methodology used in a published study [Kang, 1998] (See Figure 2). Although the goal of the current study is to attempt to replicate the blood pressure results from the IV administration of epoetin alfa in that publication, SBP will be the primary endpoint rather than MAP since SBP is the overall best predictor of future cardiovascular risk in a hypertensive population, and MAP is biased toward DBP [Agarwal, 2015].
- Acute Challenge 1 will assess whether there are any immediate effects of daprodustat or epoetin alfa on blood pressure. This assessment will also determine the ability to replicate the findings in the published study and will provide information for an interim analysis (See Section 9.3.2).
- The 8-week Hgb Maintenance Phase will replicate the management procedures planned for the Phase 3 studies as described in Section 6.4. The duration was chosen to be consistent with the timeframe in which the hypertensive effects of ESAs have been observed (i.e., 4 to 8 weeks) [Samtleben, 1988].
- Acute Challenge 2 will again assess the effects of daprodustat or epoetin alfa on BP following 8 weeks of anemia treatment utilizing the same assessment as Acute Challenge 1. The purpose of Acute Challenge 2 is to assess any BP effects of ESA administration that may be potentiated (or possibly diminished) following long-term administration of an ESA.

Figure 2 Changes in MAP after administration of rhEPO (rHuEPO) and control

Values are mean \pm SD; *P<0.05 vs. Post-HD [Kang, 1998]

4.5. Dose Justification

Daprodustat Treatment Group

- Acute Challenge 1 & 2: The dose to be used for this group will be the highest planned maintenance dose for a once-daily regimen (i.e., 24 mg) for treatment of anemia associated with CKD. In a previous GlaxoSmithKline (GSK) study (PHI112843), a single, oral dose of 150 mg daprodustat was administered to dialysis patients with no safety issues identified. For Acute Challenge 2, stringent Hgb stopping criteria and dose hold have been defined at Day 57 to minimize marked increases in Hgb.
- Hgb Maintenance Phase: Starting doses of daprodustat will be based on Hgb levels, as described in Section 6.4.1. These doses have been chosen to minimize the potential for subjects to meet Hgb stopping criteria during the initial dosing period prior to the first dose adjustment, and are based on modelling and simulation of the dose-Hgb response results from Phase 2 studies.

Epoetin alfa Treatment Group

- Acute Challenge 1 & 2: The dose to be used for this group will be the highest labelled starting dose for epoetin alfa (100 U/kg, IV) which is consistent with the epoetin alfa dose used in the published study where an acute increase in MAP with rhEPO was observed [Kang, 1998]. As subjects in this group will have been washed off ESA for 2 weeks prior to Acute Challenge 1 and only a single dose will be administered, the risk of a marked increase in Hgb levels is considered very low. For Acute Challenge 2, stringent Hgb-based stopping criteria and dose hold have been defined at Day 57 to minimize marked increases in Hgb (See Table 2).
- Hgb Maintenance Phase: The dosage of epoetin alfa during the 8-week Hgb

maintenance phase will be adjusted (if necessary) according to the local labelling in order to manage the subject's Hgb within the target range (10.0-11.0 g/dL). In a previous study (GSK Study PHI113633), HD subjects that had a 4-week ESA washout were initiated on a mean dose of rhEPO of 89 IU/kg/week (n=39), with the dose increased to a mean of 102 IU/kg/week 4 weeks later.

4.6. Benefit:Risk Assessment

Summaries of findings from both clinical and non-clinical studies conducted with daprodustat can be found in the Daprodustat Investigator's Brochure (IB) and IB Supplements, if applicable.

4.6.1. Risk Assessment

The potential risks of clinical significance including AEs of special interest (Section 7.3.1.4), and the mitigation strategies for this protocol taking into account the results of clinical and non-clinical studies with daprodustat, are outlined in Section 12.3.

4.6.2. Benefit Assessment

In clinical trials of up to 24 weeks in duration, in subjects with anemia associated with CKD, daprodustat has been shown to treat Hgb to target range. Data from prior studies with daprodustat suggest that the increases in Hgb are achieved with EPO exposure lower than those observed with rhEPO.

4.6.3. Overall Benefit:Risk Conclusion

Daprodustat demonstrates a positive benefit vs. risk based on the evidence as follows. In clinical trials up to 24 weeks in duration, daprodustat maintained Hgb to target range in subjects with anemia associated with CKD (both ND and HD) with a safety profile consistent with the patient population.

This protocol employs precautions to mitigate known and potential risks to enrolled subjects (See Section 12.3). Given these precautions, as well as the potential benefit that daprodustat holds for the treatment of anemia associated with CKD compared to the current standard, the overall benefit risk balance is considered to be positive.

5. SELECTION OF STUDY POPULATION AND WITHDRAWAL CRITERIA

Specific information regarding warnings, precautions, contraindications, adverse events, and other pertinent information on daprodustat that may impact subject eligibility is provided in the Daprodustat Investigator's Brochure and IB Supplements, if applicable.

Deviations from inclusion and exclusion criteria are not allowed because they can potentially jeopardize subject safety, the scientific integrity of the study, or regulatory acceptability. Adherence to the criteria as specified in the protocol is essential.

5.1. Hemoglobin Stability Criteria

Entry into the study requires a stable Hgb between **8.5 and 11.5 g/dL, inclusive**. This is confirmed from **two** Hgb values obtained at the Screening Visit and Washout Visit, with both values between 8.5 and 11.5 g/dL. These will be taken via a validated point-of-care device to measure Hgb (i.e., HemoCue) prior to the dialysis session of the day. The value at the Washout Visit must not have decreased by more than 1.0 g/dL from the Screening Visit value. For subjects with a three-times weekly dialysis schedule, Hgb values must not be obtained on the first dialysis session of the week (e.g., if Monday-Wednesday-Friday schedule, the study visit cannot be on Monday). For subjects with a four- to five-times weekly dialysis schedule, Hgb values can be obtained on any hemodialysis session of the week.

